1 RATIONALE

The pilot study will test the feasibility and efficacy of a novel computerized intervention. The intervention will be an add-on to the current ‘treatment as usual’ at the Burnaby Centre for Mental Health & Addiction (BCMHA) in Burnaby, BC, Canada. ‘Treatment as usual’ encompasses the full array of evidence-based treatments (Knapp 2015). But, there is still ample need to improve treatment, specifically stimulant (cocaine and methamphetamine) use disorder treatment (Newton 2013). BCMHA serves the hardest-to-treat clients with severe concurrent disorders by providing a six-month inpatient recovery program (Schütz 2013). The program focuses on clients who have not been treated successfully by locally available services. The study will be randomized and double blinded by design, but may turn out to be single-blinded, as interviewers will be exposed to both active and placebo trials and may be able to differentiate active from inactive interventions. The intervention is an adaptation of the recently developed “retraining of automatic approach” intervention, which has been shown to reduce relapses in alcohol dependent persons (Wiers 2013) and seems to be currently successfully tested in smokers (Woud 2016).

BACKGROUND

Stimulant use disorders are among the most challenging disorders, specifically in individuals suffering from concurrent disorders or also identified as dual diagnosis (Banlieu 2012). While medication is available to support the treatment of other substance use disorders (alcohol, opioids, tobacco), currently there is none to treat stimulant use disorders, such as cocaine use disorder and methamphetamine use disorder (Newton 2013). Current interventions are mainly based on education, motivational interviewing and cognitive behavioural approaches. The cognitive behavioural approach has limits in the population treated at the BCMHA, as they often suffer from mild to moderate cognitive problems, and thus may have issues in understanding complex behaviours (Homer 2008, Depp 2015). Contingency management is another evidence-based approach (Knapp 2015). All interventions are provided concurrently at BCMHA.

Treatments can be combined with CEASAR. In fact, they appear to be complementary approaches.

Recently a group in Europe developed the “retraining of automatic approach” intervention, which is not based on conscious learning, the need of the client, or the client’s understanding of her or his behaviour, but constitutes a more mechanistic training. This method was successfully applied to change drinking behaviour in a sample of alcoholic inpatients (Wiers 2010). The intervention—based on cognitive-bias modification—is straightforward, uncomplicated, and does not require “active learning based on an understanding of complex behaviours” (Wiers 2011). The intervention itself is a simple targeted computer based training for “avoidance of substances”. As opposed to the more regularly used explicit or declarative learning, an implicit non-declarative procedural learning approach is used. This approach is less dependent on an

Computerized exercise to alter stimulant approach responses (CEASAR)

individual's ability to understand their own situation-dependent behaviours, but is more of a procedural type of training such as learning to ride a bike. Participants respond to cues by initiating a distancing activity (pushing a joystick away). Positive activities in contrast, are pulled in. This differential activity trains participants to alter initial responses and "cognitive biases" (Wiers 2013).

OBJECTIVES

1.1 RESEARCH QUESTION:

1.1.1 Can the CEASAR intervention (Computerized Exercise to Alter Stimulant Approach Responses) be successfully integrated into treatment at the BCMHA?

1.1.2 Does the approach show any effectiveness in improving treatment outcomes when applied to a population of complex concurrent disorder clients at an in-patient recovery program?

1.2 HYPOTHESIS

1.2.1 The intervention will be easy to integrate into the existing program.

1.2.2 Participation in the experimental (stimulant-avoidance) condition will reduce craving (as assessed by the stimulant craving questionnaire brief version), show reduction in an automatic association of activities with stimulant use and stimulant relapses (as assessed by behaviour association questionnaires) and have reduced relapses as assessed by urine drug screens in 12 weeks following initiation of the intervention.

1.3 OBJECTIVE

Test the hypothesis and evaluate whether or not the Computerized Exercise to Alter Stimulant Approach Responses (CEASAR) can improve stimulant use disorder outcomes in a population with concurrent disorders that are difficult to treat.

2 METHODS

2.1 RESEARCH METHODS:

2.1.1 Patients

The inclusion criteria for participants are:

- Adult: Must be 19 years or older
- "Current" stimulant use disorder (cocaine, crack cocaine, amphetamine, methamphetamine, crystal meth), active before intake at BCMHA (assessed by MINI)
- Competent to consent: Must understand the consent form and give informed consent
- Proficient in English

This study will enrol both male and female subjects, and requires proficiency to read and write in English in order to understand the consent form. Additionally, patients must have been diagnosed with a stimulant use disorder (mainly cocaine use disorder, methamphetamine use disorder). Patients will be recruited at the centre using flyers and through active recruitment of clinic clients by interviewers. Once a client has indicated interest in the study, an interviewer will provide the potential participant with the consent form, review the consent form and if possible, gain informed consent from all participants. Participants will be given enough time to decide whether or not they wish to participate. They may decide to participate in the study at any time,

Computerized exercise to alter stimulant approach responses (CEASAR)

given that the study is still being conducted and that the participants will still be at the BCMHA for 12 weeks once they agree to begin the study.

Interested clients will be screened during the consent process for eligibility. In addition, participants may be excluded during the study in the case of acute crises not allowing them to regularly participate. This will be determined by the treating psychiatrist, and could arise from situations such as psychotic decompensation, an acute depressive episode, or a manic or hypomanic episode.

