2.3 INTERVENTION

Consenting patients will be randomized into 2 conditions: the active, CEASAR intervention (experimental condition) and a placebo intervention (control condition). Assessment of the outcome will be done blind to the randomization.

A randomization monitor will generate and maintain a list of random numbers. A randomization list will be run to assign either experimental or placebo intervention. The investigators will contact the randomization monitor after enrolling a participant, and the randomization monitor will generate a randomization number and communicate this number to the investigator.

Computerized exercise to alter stimulant approach responses (CEASAR)

In both cases, individuals will use joysticks to train “approaching” or “avoiding or distancing”. In the placebo condition, the stimulant cues and neutral cues will be randomized. In the treatment condition, individuals will be trained to “avoid” cues associated with stimulant use and approach “alternative” cues. Individuals will be asked to cue their activity (approach=pull versus avoid=push) based on the framing of the cue (landscape versus portrait). Alternative cues will contain a variety of objects, which will range from small articles such as a pen, to food items. Previous studies have demonstrated that outcome is independent from mode of presentation – whether it is implicit (participant not aware of what they are doing) or explicit (participant knows what they are doing).

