2.4 DURATION

A CEASAR session will last 15 minutes. Study participants will take part in three sessions per week in the first two weeks, then two sessions per week in the following 2 weeks, and then one session per week thereafter. Each patient will participate in a total of 14 sessions over a period of 8 weeks. The outcome assessment will cover 12 weeks after the initiation of the intervention (4 weeks after the last CEASAR session). While a six month follow up would be preferred, given the pilot character of the study and the average length of stay of 4 months, we decided to focus on the three-month period as a pilot.

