2.5 SAMPLE SIZE

For the pilot study we plan to recruit a minimum of 60 participants to complete 12 weeks of the pilot study. A recent review on pilot sample data suggested a sample size of 10-40 per group (Herzog 2008)³; with 30 completers at each group, we will be on the upper end of the suggested sample size.

If we recruit 10 individuals every month, we will complete recruitment in approximately 6-8 months (depending on non-completion). The plan is to complete the study in approximately one year.

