3.2 STATISTICAL ANALYSIS

Relapses: Cumulative relapses will be compared using simple t-tests. Further analysis using linear regression models will account for potential baseline differences (due to randomization). The clinical urine drug screens will provide the basis for calculating relapses.

Craving: Stimulant craving reduction (baseline versus week 12) will be compared to the placebo group, as assessed by the Stimulant Craving Questionnaire-Brief (SCQ-B) (Paliwal 2008). Statistical analysis will be similar to the primary outcome with t-test and linear regression models.

Behaviour Association scale: The scale has four dimensions, which will be analyzed separately (see above).

The study will have to be approved by the ethics committee and the PHSA research board before initiation. It will be registered with Clinical Trial at NIH.

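### The leading relapse comparison is an unadjusted t-test and the follow-up regression names no covariates, although participants can enter at different stages of their stay and a baseline urine screen is already scheduled

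*Combined protocol and SAP*

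**What the plan says.** - **Entry.** Section 2.1.1 states "They may decide to participate in the study at any time". The same sentence continues after a page header and makes this conditional on the study still running and on whether "the participants will still be at the BCMHA for 12 weeks once they agree to begin the study". The stimulant use disorder has to have been active before intake; no maximum time since intake is set.
- **Length of stay.** Section 1 describes BCMHA as "providing a six-month inpatient recovery program". Section 2.4 gives "the average length of stay of 4 months".
- **Allocation.** Section 2.3: "Consenting patients will be randomized into 2 conditions: the active, CEASAR intervention (experimental condition) and a placebo intervention (control condition"). A randomisation list is used after enrolment. Neither blocking nor stratification is mentioned.
- **Size.** Section 2.5: "we plan to recruit a minimum of 60 participants to complete 12 weeks of the pilot study", with 30 completers per group.
- **Analysis.** Section 3.2 compares cumulative relapses by t-test and adds: "Further analysis using linear regression models will account for potential baseline differences (due to randomization"). It names no covariate and does not say which of the two analyses carries the conclusion.
- **Available baseline data.** Section 3.1 has urine screening from intake and marks a baseline screen in the schedule. Section 2.2 plans chart access and lists many possible predictors of outcome, but does not list date of admission.

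**The concern.** One participant may be newly admitted and another may be well into a full treatment programme. How recently someone used, and how long they have been in care, plausibly predict relapse over the following 12 weeks. Section 3.1 itself expects few relapses, so the outcome is sparse and the arms are small.

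Three things follow:

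1. In a single trial of this size, the arms can differ by chance on a prognostic factor, and the unadjusted comparison carries that difference into the estimate.
2. Prognostic variation left in the residual costs precision.
3. A regression aimed at baseline differences, with no covariates named and a long list of candidates in section 2.2, leaves room to choose the model after looking at the data.

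Section 3.3 says the result will be used to seek support for a full trial, so the estimate should be as reliable as the data allow.

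**Working it through.** **The plan's own figure.** 2 x 30 = 60 agrees with section 2.5. The plan gives no alpha, power, effect size, SD or relapse rate, so the number cannot be derived from a power formula. It rests on a rule of thumb for pilots.

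**Entry window.** Stay minus 12 weeks:
- six-month programme: 26 - 12 = 14 weeks
- average stay: 4 x 52/12 - 12 = 5.3 weeks

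**Chance imbalance in entry time.** Assume that entry is uniform over the window, with 30 per arm. SD = window/sqrt(12); SE of the difference in arm means = SD x sqrt(2/30). If the relapse rate halves every h weeks in care (h = 8 or 12, assumed), an imbalance of 1.96 x SE gives a relative rate difference of 1 - 2^(-1.96 x SE/h).

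| Window | SD (weeks) | SE (weeks) | 95% limit (weeks) | h = 8 | h = 12 |
|---|---|---|---|---|---|
| 5.3 weeks | 1.54 | 0.40 | 0.78 | 6.5% | 4.4% |
| 14 weeks | 4.04 | 1.04 | 2.05 | 16% | 11% |

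A one-SE imbalance in the most extreme of these cases (14 weeks, h = 8) gives 1 - 2^(-1.04/8) = 8.6%.

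**Is there bias?** Trials were simulated with 30 per arm, overdispersed counts, relapse falling 3% or 10% per week since admission, and no treatment effect (5,000 trials per setting). The mean unadjusted arm difference was -0.012 to 0.005 relapse days, which is zero within simulation error. The t-test rejected in 4.4-4.6% of trials against a nominal 5%. Adjusting for time since admission alone changed the SD of the estimate by less than 2%.

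**Baseline urine result.** The documents give no positivity rate. For assumed positivity of 10%, 30% or 50%, the 95% range of the arm difference is 1.96 x sqrt(2p(1-p)/30) = 15, 23 or 25 percentage points either way. By the exact binomial, a gap of at least 6 of 30 (20 points) arises with probability 12% at p = 0.3 and 16% at p = 0.5.

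A second simulation used 20,000 trials per setting, no treatment effect, a mean of 2 relapse days, gamma-Poisson counts with shape 0.5, 1 or 2, and urine-positive participants relapsing 2, 3 or 5 times as often. All of these inputs are assumed.
- Adjustment reduced the SD of the estimate by 1-19%.
- Over all trials the t-test rejected in 4-5%.
- Among trials with a gap of 20 points or more, the t-test rejected in 5-18% and the adjusted model in 3-6%.

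**What a prognostic covariate buys.** At two-sided alpha 0.05 and 80% power (assumed), the detectable standardised difference is (1.96 + 0.84) x sqrt(2/30) x sqrt(1 - R2), where R2 is the share of outcome variance explained.

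| R2 | Detectable difference | Power at d = 0.5 |
|---|---|---|
| 0 | 0.72 | 49% |
| 0.2 | 0.65 | 58% |
| 0.5 | 0.51 | 78% |

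**The case against.** The strongest reply is that randomisation already deals with this. Allocation follows enrolment and the arms run concurrently, so recovery stage is equal in expectation, and chance imbalance is covered by the error rate of the t-test. That is correct. A reader might infer that natural recovery is mixed into the arm difference; the design does not support that, and neither do the simulated error rates.

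A reader might also infer that there is no adjustment at all, or that entry is unrestricted. Both go too far. Section 3.2 does plan a regression, and section 2.1.1 requires 12 remaining weeks.

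The size is also open to challenge. The halving times are assumptions, 16% is the top of the range, and the four-month average stay points to the smaller window for many clients. Adjusting for time since admission alone gains almost nothing in the simulated settings. This is a pilot, and a t-test is valid under randomisation.

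What remains is narrower. Validity on average does not protect the one trial that is run from a visible imbalance, and an open covariate list is a weakness whatever the size of the effect.

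**Conclusion.** The point holds as one of precision, chance imbalance and pre-specification, not of bias. Entry stage varies, no stratification is stated, the leading relapse test is unadjusted, and the regression's covariates are open, while a usable baseline value is already collected.

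For entry time alone, the distortion at the 95% limit is about 4-7% (5-week window) to 11-16% (14-week window), conditional on uniform entry and a rate that halves every 8-12 weeks. The baseline urine result probably matters more, with a gain that depends on how strongly it predicts relapse: from negligible to about a fifth of the SD under the assumptions shown. No figure in the documents allows a narrower range. The issue is modest, but the remedy is nearly free and worth adopting before any outcome data are examined.

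**What to change.** In section 3.2, name the leading relapse analysis: a linear regression of relapse days on arm and the baseline urine stimulant result (positive or negative), plus weeks from BCMHA admission to randomisation if the chart supplies the admission date. State that these covariates are included whether or not the arms look imbalanced. Keep the unadjusted t-test as a supporting analysis, and label any model using other factors from section 2.2 as exploratory.

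Recruitment and the assessment schedule do not change. The baseline screen is already in the section 3.1 schedule. Admission date is not among the chart items listed in section 2.2, so it should be added there if it is to be used. With 60 participants, residual degrees of freedom fall from 58 for the t-test to 57 with one covariate or 56 with two.

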2.2 MEASURES

The information and consent form will include information regarding access to clinical documentation to complete the characterization of individuals including socio-demographic data, clinical diagnoses, use history, medication, and cognitive characterization. All participant clients are well characterized within the treatment program at BCMHA. We will access data from the treatment provider, complement missing data and add assessments, such as a cognitive assessment component (including working memory, motor inhibition, and spatial memory). Access to clinical information will be limited to the client's current treatment program. We are thus in a position to identify factors (socio-demographics, mental disorders, substance use disorders, cognitive characteristics, smoking history, etc.) associated with treatment outcome.

During the appointment, participants will complete a battery of questionnaires as listed in the study protocol. Participants will complete questionnaires using a tablet, unless they request a paper survey. The Qualtrics system contracted through UBC and approved by UBC for ethical privacy and data storage practices, will be used for completing questionnaires and chart reviews. This will reduce the need for double data entry, reducing the overall cost and assuring data quality.

Outcome measures are:

- *Craving as assessed by the stimulant craving questionnaire-brief (Paliwal 2008).*
- *Behavioural association as assessed by the behaviour association scale, which measures the degree to which substance use is associated with a number of different situations (Krank 2010).*
- *Relapse to use as identified by self-report and regular urine drug screen.*

2.3 INTERVENTION

Consenting patients will be randomized into 2 conditions: the active, CEASAR intervention (experimental condition) and a placebo intervention (control condition). Assessment of the outcome will be done blind to the randomization.

A randomization monitor will generate and maintain a list of random numbers. A randomization list will be run to assign either experimental or placebo intervention. The investigators will contact the randomization monitor after enrolling a participant, and the randomization monitor will generate a randomization number and communicate this number to the investigator.

Computerized exercise to alter stimulant approach responses (CEASAR)

In both cases, individuals will use joysticks to train “approaching” or “avoiding or distancing”. In the placebo condition, the stimulant cues and neutral cues will be randomized. In the treatment condition, individuals will be trained to “avoid” cues associated with stimulant use and approach “alternative” cues. Individuals will be asked to cue their activity (approach=pull versus avoid=push) based on the framing of the cue (landscape versus portrait). Alternative cues will contain a variety of objects, which will range from small articles such as a pen, to food items. Previous studies have demonstrated that outcome is independent from mode of presentation – whether it is implicit (participant not aware of what they are doing) or explicit (participant knows what they are doing).

Similar to the alcohol cues and the tobacco cue based studies, which have been established, we will use a mix of validated standard cues and locally relevant cues to cover a range of potential cues associated with crystal meth and crack cocaine use. The cues will be partially visual (e.g. pictures of rocks, pipes, needles, etc.) and partially textual (e.g. eight ball, rock, etc.). For the approach condition, we will use the neutral and positive cues (e.g. an apple or a pencil) applied in previous studies. Patients will sit comfortably with a joystick while pictures are presented on a computer screen. Patients will be presented with pictures, pulling pictures in a portrait format and pushing pictures in a landscape format. In the experimental condition, pushed pictures will exclusively be stimulant use-related pictures. In the control condition, stimulant use-related pictures will be equally divided into push and pull conditions. Previous studies have used this format, and we have already implemented two workstations with this specific joystick-driven program.

2.4 DURATION

A CEASAR session will last 15 minutes. Study participants will take part in three sessions per week in the first two weeks, then two sessions per week in the following 2 weeks, and then one session per week thereafter. Each patient will participate in a total of 14 sessions over a period of 8 weeks. The outcome assessment will cover 12 weeks after the initiation of the intervention (4 weeks after the last CEASAR session). While a six month follow up would be preferred, given the pilot character of the study and the average length of stay of 4 months, we decided to focus on the three-month period as a pilot.

2.5 SAMPLE SIZE

For the pilot study we plan to recruit a minimum of 60 participants to complete 12 weeks of the pilot study. A recent review on pilot sample data suggested a sample size of 10-40 per group (Herzog 2008)³; with 30 completers at each group, we will be on the upper end of the suggested sample size.

If we recruit 10 individuals every month, we will complete recruitment in approximately 6-8 months (depending on non-completion). The plan is to complete the study in approximately one year.

2.6. COMPENSATION

Participants will be compensated with \$10 for every assessment (lasting less than one hour) and \$5 for participation in the intervention (lasting 15 min) independent of study completion, in the form of a gift card or voucher. Thus, the client can accumulate an upper limit of \$110. As clients will be compensated using the contingency management program at BCMHA, funding will support this program, allowing the client to receive “rewards” of his or her choice, but not monetary compensation. If preferred by the participant, we will alternatively compensate in the

Computerized exercise to alter stimulant approach responses (CEASAR)
form of a gift card.

